2.2 Secondary Objectives

1. To evaluate the narcotics administration of patients 6 weeks after POAmCRT (Arm 1).
2. To determine the disease recurrence rate at 24 months post-treatment in each arm.

3. To determine progression free survival (PFS) and overall survival (OS) for each arm.
4. To evaluate the proportion of PEG tube placements in each arm.
5. To determine the serum creatinine changes in patients receiving POAmCRT (Arm 1).

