5.6 Follow-Up Assessments after Adjuvant Therapy

Follow-up assessments will be planned at the following time points; actual follow up times may vary due to patient logistics and compliance:

- 6 weeks (+/- 1 week) following completion of adjuvant therapy
- 4 months (+/- 2 weeks) following completion of adjuvant therapy
- 6, 12, 18, 24, 30, 36, 48, and 60 months (+/- 6 weeks) following completion of adjuvant therapy
- annually thereafter for 5 years (total follow-up 10 years)

Patients with disease progression will only be followed for survival and will not stay on the above follow-up schedule. Their follow-up schedules will then be at the discretion of the investigator.

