5.6.3 Six to Sixty Month (+/- 6 weeks) Assessments

1. Physical examination and weight (kg).
2. Documentation of ECOG performance status.
3. Documentation of narcotic and PEG tube usage.
4. Completion of QOL questionnaires (to occur at 6, 12 and 24 month visits only).
5. CT scan of neck and chest (IV contrast preferred) to be done at 6, 12, 18, 24, and 36 months (+/- 6 weeks) following completion of therapy. CXR (PA and Lateral) may be substituted for CT chest if unable to obtain the latter.
6. OPTIONAL: Speech and swallowing assessment (to occur at 6, 12, and 24 month visits only). These will include MBS at 6 months post-adjuvant therapy, PSS-HN questionnaires at 6, 12, and 24 months, and Fiberoptic Endoscopic Evaluation of Swallowing (FEES) as clinically indicated.

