10.4.4 Endpoint Analysis

The primary endpoint is percent weight loss. Weight (kg) will be collected weekly during radiation within each arm. The percent weight loss from the baseline is calculated at any post-baseline. The generalized estimating equation (GEE) model with identity link function will be used to analyze this percent weight loss data, in which the correlation among the repeated measures from the same patient need be considered. The autoregressive

of first order as working correlation structure will be used. The GEE model includes baseline weight and time points. The p-value is estimated to assess whether the percentages of weight loss across all time points are different. Least square means for percent weight loss at each time point and mean differences between any time points will be estimated, and their standard errors will be calculated within the use of GEE sandwich method when accounting for within-patient correlation.

The secondary endpoints include proportion of PEG tube placements for all enrolled patients, the serum creatinine changes in patients receiving POAmCRT, proportion of the narcotics administration of patients 6 weeks after POAmCRT, and RFS. Proportions of PEG tube placements for all enrolled patients and the narcotics administration of patients 6 weeks after POAmCRT and their associated 95% confidence intervals will be calculated assuming a binomial distribution²³. The serum creatinine is measured at the baseline and six weeks after POAmCRT. The paired t-test will be considered to test the change.

Disease recurrence rate at 24 months post-treatment (DRR-24) in each arm is calculated for each arm. The proportion and 95% CI from binomial distribution will be shown for Arm 1. If 95% upper CI is smaller than 20%, then the risk of disease recurrence is deemed as acceptable. If 95% lower CI is larger than 20%, then the risk of disease recurrence is deemed as unacceptable. Given our small sample size, there are some uncertainties. Therefore, we do not test the hypothesis about (DRR-24) but provide a preliminary data for planning future studies.

PFS will be calculated from the date of surgery to the date of progression, death of any cause, or last known date alive. OS will be calculated from the date of surgery to the date of death or last known date alive. PFS and OS will be evaluated using Kaplan Myer.

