11.0 DATA SUBMISSION SCHEDULE

Case report forms with appropriate source documentation will be completed according to the schedule listed in this section.

Case Report Form	Submission Schedule
Original Consent Form	Prior to registration
On-Study Form	Prior to starting treatment
Surgery Form	Time of surgery
QOLs Forms	Baseline Interim assessment Day 1 of RT (-7/+0) Day 22 after start of RT (Arm 1 & 2 +/- 2 days; Arm 3 +/- 5 days) Day 36 after start of RT (Arm 1 & 2 +/- 2 days; Arm 3 +/- 5 days) 6 weeks after completion of adjuvant therapy 4 months after completion of adjuvant therapy 6 months after completion of adjuvant therapy 12 months after completion of adjuvant therapy 24 months after completion of adjuvant therapy
Toxicity Form	Continuous
Weight Form	Baseline, weekly during treatment, and at each follow-up visit
Treatment Summary Form	Completion of treatment
Follow Up Form Narcotics Form PEG Form	6 weeks, 4 months, 6 months, 12 months, 18 months, 24 months, 30 months, 36 months, and 48 months after the completion of adjuvant therapy
RECIST Form	Baseline, 6 weeks after completion of adjuvant therapy, and 6 months after completion of adjuvant therapy

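### PFS is censored at the last date known alive, so any follow-up after a patient's last disease assessment counts as progression-free; the bias, where it arises, is upward and probably small

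*Combined protocol and SAP*

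**What the plan says.** Section 10.4.4 defines PFS in one sentence: "PFS will be calculated from the date of surgery to the date of progression, death of any cause, or last known date alive". The next sentence gives OS the same end of follow-up: "OS will be calculated from the date of surgery to the date of death or last known date alive". The analysis is descriptive: "PFS and OS will be evaluated using Kaplan Myer". PFS is a secondary objective (Section 2.2): "To determine progression free survival (PFS) and overall survival (OS) for each arm".

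No other section gives PFS a different censoring date, ties it to a disease assessment, or says how missed assessments are handled.

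The follow-up plan bears on when the two dates can differ:

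- Sections 5.6.1 to 5.6.4 and the calendar in Section 14.2 put a physical examination at every follow-up visit, including the annual ones ("annually thereafter for 5 years (total follow-up 10 years").
- Planned imaging is shorter. After the neck CT at six weeks, Section 5.6.3 has "CT scan of neck and chest (IV contrast preferred) to be done at 6, 12, 18, 24, and 36 months".
- Section 5.6 moves patients to survival-only follow-up after progression, when their PFS event has already occurred. It also allows that "actual follow up times may vary due to patient logistics and compliance".
- Section 11.0 schedules the RECIST form at "Baseline, 6 weeks after completion of adjuvant therapy, and 6 months after completion of adjuvant therapy" and the follow-up form up to 48 months.

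**The concern.** For OS, the last date known alive is the right censoring date, because being alive is the whole of the outcome. For PFS it is only half of it. Suppose a patient was last examined at month 12 and is confirmed alive by telephone at month 30. The rule adds 18 months of progression-free time (30 - 12) that nobody observed. The patient stays in the Kaplan-Meier risk set, and a recurrence in that interval is either missed or shows up later as a death.

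The error runs in one direction. Deaths still count as events, so a missed recurrence removes or postpones an event and never adds one. A trial of reduced adjuvant therapy is meant to keep relapse low (Section 1.9), and an optimistic tilt in a disease-control endpoint is the unwelcome direction. What is at stake is the accuracy of a descriptive PFS curve per arm.

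**Working it through.** **The plan's own figures.** The plan states no sample size, event count or expected rate for PFS, so there is no PFS figure to reproduce. The Arm 1 sample size in Section 10.2 supplies the scale. With a difference of 7.39 - 3.7 = 3.69 points, an SD of 5.46 and a two-sided 5% one-sample t test, power is 79.6% at n=19 and 81.8% at n=20. That confirms 20 evaluable patients, and 20/0.85 = 23.5 gives 24 enrolled.

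**Inputs from Section 1.9.** Historical recurrence is 10%, with 89% of it by 24 months, so 24-month recurrence is 0.10 × 0.89 = 8.9%. The upper threshold is 20%.

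**Assumptions not in the documents.** A fraction f of patients stops disease assessment at a time uniform over 0-24 months but stays known alive. Stopping is independent of recurrence, and later recurrences in these patients go unseen. Other-cause deaths are ignored at first. Time runs from the end of therapy, because the Section 1.9 figures do; the PFS clock starts at surgery, at least 8 weeks earlier in Arm 1 (28 days to the start of RT plus 4 weeks of RT).

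**Closed form.** Let S(t) be true PFS with exponential recurrence. Under the plan's rule nobody is censored before 24 months, and a patient who stops at time u counts as an event only if recurrence came before u. Hence

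PFS24(plan) - S(24) = f × [mean of S(u) over 0-24 - S(24)], where mean S = (1 - S(24)) / (-ln S(24)).

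- At 8.9%: mean S = 0.089/0.0932 = 0.9548, and the bracket is 0.9548 - 0.911 = 0.0438.
- At 20%: mean S = 0.200/0.2231 = 0.8963, and the bracket is 0.8963 - 0.800 = 0.0963.

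**Simulation.** As a second check, 400,000 patients per scenario were simulated. Recurrence was detected only at the next attended visit on the protocol schedule.

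| Fraction stopping | 8.9%: closed form | 8.9%: simulation | 20%: closed form | 20%: simulation |
|---|---|---|---|---|
| 10% | 0.44 | not run | 0.96 | not run |
| 15% | 0.66 | 0.8 | 1.44 | 1.8 |
| 30% | 1.31 | 1.6 | 2.89 | 3.6 |

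(Overstatement of 24-month PFS, in percentage points.)

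The simulated values are somewhat larger. One reason is that a recurrence arising between the last attended visit and the stopping time is also missed. With no assessment gap, the plan's rule and censoring at last assessment agree exactly. With 5% other-cause death at three years and 30% stopping, the overstatement is 89.6 - 88.05 = 1.55 points at 8.9% recurrence, so deaths change little.

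**Scale.** The standard error at n=20 is √(0.911 × 0.089/20) = 6.4 points. One missed recurrence among 20 patients is 1/20 = 5 points.

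**Check on the remedy.** Take 30% stopping, 8.9% recurrence and 5% three-year death.

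| PFS rule | 24 months | 60 months |
|---|---|---|
| Complete assessment (truth) | 88.05% | 82.61% |
| Plan's rule | 89.60% | 84.40% |
| Last assessment; later deaths not counted | 88.03% | 82.61% |
| Last assessment; all later deaths counted | 87.47% | 80.25% |

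The third row matches the truth because stopping was assumed independent of outcome. The fourth is low by 0.6 points at 24 months and by 2.4 points at 60 months.

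**The case against.** The strongest reply is that the plan leaves little room for the two dates to separate. Event-free patients remain on the visit schedule, every visit includes a physical examination, and Section 5.10 keeps patients who stop treatment early on the study calendar. When the last contact is one of those visits, the last date known alive is also the date of an assessment. This stands. The bias is conditional, and the documents give no rate for the condition.

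Three stronger readings are tempting, and the documents do not support them:

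- **That the rule inflates PFS in every arm as a matter of fact.** It does so only where someone is known alive beyond the last assessment. The Section 5.6 remark on varying follow-up times concerns the timing of visits. It does not say that patients leave assessment while still being traced.
- **That the end of planned CT at 36 months opens a growing gap.** If a protocol examination counts as a disease assessment, examinations continue through the annual visits and attended visits leave no gap. Late follow-up is checked clinically, though not by planned imaging.
- **That the Arm 1 recurrence criterion is compromised.** Section 10.4.4 compares the binomial 24-month recurrence rate with 20%. PFS carries no hypothesis, threshold or decision.

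What survives the reply is the wording of the rule. It names a date that is not a disease assessment, and nothing else in the plan corrects it for a patient who misses visits but is known to be alive.

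**Conclusion.** The point holds as a minor correction to the analysis text. For patients known alive after their last disease assessment, Section 10.4.4 counts unassessed time as progression-free. Relative to complete assessment, that either introduces no bias or biases PFS upward.

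With 10-30% of patients in that position, 24-month PFS is overstated by about 0.4-1.3 points at the historical recurrence rate and 1.0-2.9 points at 20%. The simulation puts the 30% figures at 1.6 and 3.6 points. All of these rest on an assumed stopping fraction, uniform stopping times and independence from recurrence. They are small beside the sampling error at n=20. A small sample does not remove a one-directional error, but here the error does not bear on the primary endpoint or on the 20% recurrence criterion.

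The wording of the rule is certain. Whether it will produce a visible overstatement in this trial cannot be judged from the documents.

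**What to change.** In Section 10.4.4:

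1. Censor PFS, for patients without progression or death, at the date of the last disease assessment, defined as a protocol physical examination or CT.
2. State how deaths after missed assessments are counted. This matters: in the check above, counting all of them while censoring other patients at the last assessment gave a downward error of 2.4 points at 60 months, larger than the plan rule's upward error there (84.40 - 82.61 = 1.8 points).
3. Keep the last date known alive as the censoring date for OS only.
4. Confirm that the case report forms capture assessment dates. Section 11.0 lists when forms are due, not their fields. The RECIST form ends at 6 months and the follow-up form at 48 months, so it should not be assumed that the dates are already collected.

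The cost is a sentence or two of analysis text and a check of the forms, with no new visits, scans or patients. The downside is slightly shorter PFS follow-up and, if all late deaths count as events, a slight downward bias at 24 months that grows with longer follow-up.

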11.0 DATA SUBMISSION SCHEDULE

Case report forms with appropriate source documentation will be completed according to the schedule listed in this section.

Case Report Form	Submission Schedule
Original Consent Form	Prior to registration
On-Study Form	Prior to starting treatment
Surgery Form	Time of surgery
QOLs Forms	Baseline Interim assessment Day 1 of RT (-7/+0) Day 22 after start of RT (Arm 1 & 2 +/- 2 days; Arm 3 +/- 5 days) Day 36 after start of RT (Arm 1 & 2 +/- 2 days; Arm 3 +/- 5 days) 6 weeks after completion of adjuvant therapy 4 months after completion of adjuvant therapy 6 months after completion of adjuvant therapy 12 months after completion of adjuvant therapy 24 months after completion of adjuvant therapy
Toxicity Form	Continuous
Weight Form	Baseline, weekly during treatment, and at each follow-up visit
Treatment Summary Form	Completion of treatment
Follow Up Form Narcotics Form PEG Form	6 weeks, 4 months, 6 months, 12 months, 18 months, 24 months, 30 months, 36 months, and 48 months after the completion of adjuvant therapy
RECIST Form	Baseline, 6 weeks after completion of adjuvant therapy, and 6 months after completion of adjuvant therapy

12.0 DATA AND SAFETY MONITORING

In compliance with the Washington University Institutional Data and Safety Monitoring Plan, the Principal Investigator will provide a Data and Safety Monitoring (DSM) report to the Washington University Quality Assurance and Safety Monitoring Committee (QASMC) semi-annually beginning six months after accrual has opened (if at least five patients have been enrolled) or one year after accrual has opened (if fewer than five patients have been enrolled at the six-month mark).

The Principal Investigator will review all patient data at least every six months, and provide a semi-annual report to the QASMC. This report will include:

- HRPO protocol number, protocol title, Principal Investigator name, data coordinator name, regulatory coordinator name, and statistician
- Date of initial HRPO approval, date of most recent consent HRPO approval/revision, date of HRPO expiration, date of most recent QA audit, study status, and phase of study
- History of study including summary of substantive amendments; summary of accrual suspensions including start/stop dates and reason; and summary of protocol exceptions, error, or breach of confidentiality including start/stop dates and reason
- Study-wide target accrual and study-wide actual accrual

- Protocol activation date
- Average rate of accrual observed in year 1, year 2, and subsequent years
- Expected accrual end date and accrual by cohort
- Objectives of protocol with supporting data and list the number of participants who have met each objective
- Measures of efficacy
- Early stopping rules with supporting data and list the number of participants who have met the early stopping rules
- Summary of toxicities separated by cohorts
- Abstract submissions/publications
- Summary of any recent literature that may affect the safety or ethics of the study

The study principal investigator and Research Patient Coordinator will monitor for serious toxicities on an ongoing basis. Once the principal investigator or Research Patient Coordinator becomes aware of an adverse event, the AE will be reported to the HRPO and QASMC according to institutional guidelines.

14.0 STUDY CALENDARS

14.1 Baseline and Treatment Calendar

	Baseline ⁴	Surgery	Interim Assessment (14 to 42 days post-surgery)	Post-operative Adjuvant Chemotherapy/Radiation		
				D1	D2 ¹²	D36 ¹²
Informed consent	X					
Laryngoscopy ¹	X					
PE w/ECOG PS	X		X	X	X	X
Weight	X			X ⁸		X ⁸
Comorbidity index	X		X			
CBC	X		X	X	X	X
CMP + magnesium	X					
BMP + magnesium			X	X	X	X
PT/PTT	X		X			
Pregnancy test ²	X					
Neck CT w/contrast	X					
FDG-PET/CT	X					
QOLs ³	X		X	X ¹³	X	X
OPTIONAL: Speech & Swallow Study ¹⁰	X		X	X ¹¹	X	X ⁹
Surgery ⁵		X ⁵				
Rad Tx Planning			X			
IMRT or IMPT ⁶				X		X ⁹
Arms 1 & 3: Cisplatin ⁷				X ⁷	X ⁹	X ⁹
AE assessment	X		X	X	X	X
Documentation of narcotic usage				X	X	X

1. Assessment of primary tumor site will be done by laryngoscopy performed in the office or operating room.

2. In women of childbearing potential only.

3. FACT H&N, M.D. Anderson Dysphagia Inventory, University of Michigan Xerostomia Index, Scale of Subjective Total Taste Acuity, and Neck Dissection Impairment Index.

4. Baseline assessments must take place no more than 35 days prior to enrollment, with the exception of PET scans (within 42 days).

5. See Section 5.2.

6. Arms 1 and 2: Once daily M-F, with one BID treatment each week for 4200 cGy in 21 fractions. Arm 3: Once daily M-F for 6000 cGy in 30 fractions

7. To be given during initial 5 doses of POART. See Section 5.4.1 for fluids and premedications. On Arm 3, cisplatin will only be given to patients with pathologic evidence of positive margins or ECE (see section 1.9).

8. Collect weight weekly during Radiation.

9. Arm 3 only.

10. Modified barium swallow and the Performance Status Scale for Head and Neck Cancer (PSS-HN) questionnaire.

11. Modified barium swallow NOT needed on this day.

12. Arm 1 & 2 +/- 2 days; Arm 3 +/- 5 days

13. -7/+0 days

14.2 Follow-up Calendar

	Short Term Follow-up		Long-Term Follow-Up							Annually Thereafter ⁵
			Months post-end of CRT ³							
	6 weeks post-end of tx (+/- 1 week)	4 months post-end of tx (+/- 2 weeks)	6	12	18	24	30	36	48	
PE w/ECOG PS + Weight	X	X	X	X	X	X	X	X	X	X
BMP	X									
Neck CT w/contrast	X		X	X	X	X		X		
Chest CT w/contrast ²			X	X	X	X		X		
QOLs	X	X	X	X		X				
OPTIONAL: Speech & Swallow Assessment		X	X	X ⁴		X ⁴				
Documentation of narcotic usage	X	X	X	X	X	X	X	X	X	
Documentation of PEG tube usage	X	X	X	X	X	X	X	X	X	
AE assessment	X									

1. FACT H&N, M.D. Anderson Dysphagia Inventory, University of Michigan Xerostomia Index, Scale of Subjective Total Taste Acuity, and Neck Dissection Impairment Index.

2. Chest x-ray (PA and Lateral) may be substituted for chest CT if it is unable to be obtained (i.e. insurance issues)

3. +/- 6 week window

4. Modified barium swallow not required

5. For 5 years (total of 10 years of follow-up)

APPENDIX 1: ECOG Performance Status

ECOG PERFORMANCE STATUS*	
Grade	ECOG
0	Fully active, able to carry on all pre-disease performance without restriction.
1	Restricted in physically strenuous activity but ambulatory and able to carry out work of a light or sedentary nature, e.g., light house work, office work.
2	Ambulatory and capable of all self-care but unable to carry out any work activities. Up and about more than 50% of waking hours.
3	Capable of only limited self-care, confined to bed or chair more than 50% of waking hours.
4	Completely disabled. Cannot carry on any self-care. Totally confined to bed or chair.
5	Dead.

* As published in Am. J. Clin. Oncol:

APPENDIX 2: Comorbidity Index

<http://otooutcomes.wustl.edu/Research/Research-Focus/Cancer/Comorbidity-Calculator>

If a patient has Grade 2 events in more than one system, their overall score will be Grade 3

APPENDIX 3: FACT-H&N (Version 4)

Below is a list of statements that other people with your illness have said are important. **Please circle or mark one number per line to indicate your response as it applies to the past 7 days.**

PHYSICAL WELL-BEING		Not at all	A little bit	Some-what	Quite a bit	Very much
GP1	I have a lack of energy	0	1	2	3	4
GP2	I have nausea	0	1	2	3	4
GP3	Because of my physical condition, I have trouble meeting the needs of my family	0	1	2	3	4
GP4	I have pain	0	1	2	3	4
GP5	I am bothered by side effects of treatment	0	1	2	3	4
GP6	I feel ill	0	1	2	3	4
GP7	I am forced to spend time in bed	0	1	2	3	4
SOCIAL/FAMILY WELL-BEING		Not at all	A little bit	Some-what	Quite a bit	Very much
GS1	I feel close to my friends	0	1	2	3	4
GS2	I get emotional support from my family	0	1	2	3	4
GS3	I get support from my friends	0	1	2	3	4
GS4	My family has accepted my illness	0	1	2	3	4
GS5	I am satisfied with family communication about my illness	0	1	2	3	4
GS6	I feel close to my partner (or the person who is my main support)	0	1	2	3	4
Q1	Regardless of your current level of sexual activity, please answer the following question. If you prefer not to answer it, please mark this box  and go to the next section.					
GS7	I am satisfied with my sex life	0	1	2	3	4

Please circle or mark one number per line to indicate your response as it applies to the past 7 days.

EMOTIONAL WELL-BEING		Not at all	A little bit	Some- what	Quite a bit	Very much
GE1	I feel sad	0	1	2	3	4
GE2	I am satisfied with how I am coping with my illness	0	1	2	3	4
GE3	I am losing hope in the fight against my illness	0	1	2	3	4
GE4	I feel nervous	0	1	2	3	4
GE5	I worry about dying	0	1	2	3	4
GE6	I worry that my condition will get worse	0	1	2	3	4

FUNCTIONAL WELL-BEING		Not at all	A little bit	Some- what	Quite a bit	Very much
GF1	I am able to work (include work at home)	0	1	2	3	4
GF2	My work (include work at home) is fulfilling	0	1	2	3	4
GF3	I am able to enjoy life	0	1	2	3	4
GF4	I have accepted my illness	0	1	2	3	4
GF5	I am sleeping well	0	1	2	3	4
GF6	I am enjoying the things I usually do for fun	0	1	2	3	4
GF7	I am content with the quality of my life right now	0	1	2	3	4

Please circle or mark one number per line to indicate your response as it applies to the past 7 days.

ADDITIONAL CONCERNS		Not at all	A little bit	Some- what	Quite a bit	Very much
H&N1	I am able to eat the foods that I like	0	1	2	3	4
H&N2	My mouth is dry	0	1	2	3	4
H&N3	I have trouble breathing	0	1	2	3	4
H&N4	My voice has its usual quality and strength	0	1	2	3	4
H&N5	I am able to eat as much food as I want	0	1	2	3	4
H&N6	I am unhappy with how my face and neck look	0	1	2	3	4
H&N7	I can swallow naturally and easily	0	1	2	3	4
H&N8	I smoke cigarettes or other tobacco products	0	1	2	3	4
H&N9	I drink alcohol (e.g. beer, wine, etc.)	0	1	2	3	4
H&N 10	I am able to communicate with others	0	1	2	3	4
H&N 11	I can eat solid foods	0	1	2	3	4
H&N 12	I have pain in my mouth, throat or neck	0	1	2	3	4

